5.3 Exploratory Outcomes

5.3.1 *Domain: Physician evaluated changes in disease activity*

Timeframe: 0 to 12 weeks

Measurement:

- Itemized Physician evaluated changes in measures of SLE on a scale from 0-22 that account for partial improvements in condition. Evaluated by the Systemic Lupus Erythematosus Disease Activity Index 2000 Responder Index-50 (SRI-50)⁴¹.
- Disease activity as evaluated by a physician familiar with SLE diagnosis based on physical examination and patient history on a scale of 0 to 100, higher score indicating more active disease.

5.3.2 *Domain: Patient reported outcome measures*

Timeframe: 0 to 12 weeks, and again as an exploratory analysis, at 1, 2 and 3 months following the intervention.

Measurements:

- Total fatigue as assessed by the participant on a visual analog scale from 0-100, higher scores equal less fatigue.
- Total pain on a visual analog scale of 0-100, higher scores equal more pain (worse).
- Quick systemic lupus activity questionnaire (Q-SLAQ) as reported by the Q-SLAQ questionnaire (translated to Danish by author MLA)⁴². Possible scores range from 0 to 33, with higher scores representing more active SLE (worse)

- SLE activity on a visual analog scale of 0-10 higher scores equal more active disease (worse).

5.3.3 *Domain: Kidney disease*

Timeframe: 0 to 12 weeks

Measurements:

- Measured by proteinuria.
- Measured by plasma-creatinine.

5.3.4 *Domain: Body Composition*

Timeframe: 0 to 12 weeks

Measurements:

By DEXA scan:

- Total adipose tissue by weight/percentage.
- Android adipose tissue by weight/percentage.
- Gynooid adipose tissue by weight/percentage.
- Total lean mass by weight.
- Bone Mass density by weight per area.

By tape measure

- Waist to height ratio

5.3.5 *Domain: Lung Function*

Timeframe: 0 to 12 weeks

Measurements:

By dynamic spirometry

- Forced Expiratory Volume at 1 second (FEV1) as volume / percentage of expected.
- Forced vital capacity as volume / percentage of expected.
- Forced expiratory volume by forced vital capacity – ratio between volumes / percentages.
- Total lung capacity – volume / percentage of expected.
- Residual Lung volume – volume / percentage of expected.
- Alveolar volume – volume / percentage of expected.
- Diffusing capacity for carbon mono-oxide – volume / percentage of expected.
- Carbon mono-oxide transfer coefficient – diffusing capacity per liter of lung volume – ratio / percentage of expected

5.3.6 *Domain: Metabolic adaptations*

Timeframe: 0 to 12 weeks

Measurements: Measured during an OGTT at 0, 15, 30, 60, 90, and 120 minutes following consumption of 83g of glucose in 250mL of water.

- Plasma concentration of glucose.
- Plasma concentration of insulin.
- Plasma concentration of pro-insulin c-peptide.
- Overall changes in the curves will be compared.
- Matsuda Index will be calculated
- Disposition Index will be calculated
- AUC will be calculated

Measurements: Measured following an overnight fast, at the 0 minute mark of the OGTT

- Plasma concentration of total cholesterol
- Plasma concentration of triglycerides
- Plasma concentration of LDL-cholesterol
- Plasma concentration of VLDL-cholesterol
- Plasma concentration of HDL-cholesterol

5.3.7 *Domain: Peripheral Capillary adaptations*

Timeframe: 0 to 12 weeks

Measurements: Measured by nailfold capillaroscopy by a trained physician, twice before and twice after intervention. Analyzed for:

- Capillary density - score of 1-4, higher scores equal fewer capillaries
- Average capillary width – in μm
- Average capillary length – in μm
- Count of avascular areas - score of 1-4, higher scores indicate more avascular areas
- Capillary disorganization - score of 1-4, higher scores indicate more disorganization
- Microhemorrhages – count per finger
- Bushy capillaries – average number per millimeter
- Mega capillaries – average number per millimeter
- Meandering capillaries – average number per millimeter
- Tortuous capillaries – average number per millimeter
- Other findings – physicians comment

5.3.8 *Domain: Cardiac adaptations*

Timeframe: 0 to 12 weeks

Measurements:

Measured bedside:

- Systolic blood pressure at rest
- Diastolic blood pressure at rest
- Heart rate at rest

Measured by echocardiography by a trained physician

- Left ventricular end-diastolic volume
- Left atrial end-diastolic volume
- Global longitudinal strain
- Stroke volume
- Left ventricular ejection fraction
- Left ventricular mass
- Coronary perfusion reserve

Measured by ^{82}Rb -rest-stress-Pet-CT on a subset of patients (30-40 depending on patient opt-in), stress will be conducted with low-dose adenosine:

- Coronary perfusion reserve
- Myocardial flow reserve
- Ventricular volumes at rest and stress
- Atrial volumes at rest and stress
- Ventricular and atrial ejection fractions at rest and stress
- Splenic response ratio
- Splenic stress-to-rest intensity ratio
- Heart rate at rest and stress
- Rate pressure product
- Systolic blood pressure at rest and stress
- Cardiovascular resistance at rest and stress

5.3.9 *Domain: Free-living physical activity*

Timeframe: 0 to 12 weeks

Measurements:

- Free-living physical activity measured using axial accelerometer-based physical activity monitors (AX3; Axivity, Newcastle upon Tyne, UK) for a 5 day period

5.3.10 *Domain: Acute exercise bout*

Timeframe: 0 to 12 weeks

Description: Subjects arrive fasted and then undergo a 45minute exercise sessions consisting of 4 intervals of 4 minutes and interspaced with active rest, starting with a 10 minute warmup and ending with a 10 minute cooldown, peripheral blood will be sampled 9 times at the following timepoints (in minutes): -5 (before going on the bike), 0 (on the bike before first pedaling), 10 (after warmup), 14 (after first interval), 35 (after last interval), 45 (after cooldown), 60 (resting for 15 minutes after getting off the bike), 90 (resting for 45 minutes after getting off the bike), and 105 (resting for 60 minutes after getting off the bike)

Measurements: concentration in peripheral blood:

- High Sensitivity C-Reactive Protein
- Interleukin-6
- Soluble Interleukin-6 receptor
- Interleukin-1
- Interleukin-10
- Interferon α
- Interferon γ
- Hemoglobin
- Thrombocytes
- Sodium
- Potassium
- Chloride
- Hematocrit
- Ferritin
- Leukocyte Differential count

Measurements: Subject adaptations to exercise

- Heart rate (continuous throughout session)
- Resistance in high intensity intervals
- Subject exhaustion by Borg Scale (6-20 higher scores equal more exhaustion) during, warmup, each interval and following cooldown.

5.3.11 *Domain: Pro- and anti-inflammatory related mRNA expression*

Timeframe: 0 to 12 weeks

Type 1 interferon induced changes to exercise adaptations in systemic lupus erythematosus patients.

Description: as with the secondary outcome, mRNA segments of genes related to the following signaling pathways will be measured using Nanostring™

Measurements:

- Expression related to IFN- β
- Expression related to IFN Gamma
- Expression related to TNF
- Expression related to IL-6

5.3.12 Domain: Dietary diaries

Timeframe: 0-2 to 12-14 weeks

Description: Subjects will be tasked to fill in dietary diaries for three consecutive representative days at baseline and followup. Using standard calculations energy intake and macronutrients will be calculated from this diary.

Measurements:

- Energy intake (kJ/day)
- Carbohydrate intake (g/day)
- Lipid intake (g/day)
- Protein intake (g/day)
- Other intake (categorical)

5.3.13 Domain: Muscular adaptation

Timeframe: 0 to 12 weeks

Description: A subset of volunteering subjects who will undergo muscle biopsy can deliver baseline and followup muscular biopsies

Measurements:

- Muscle Biopsy transcriptomic analysis of genes related to TNF, IL-6, IFN alpha, beta and Gamma signalling.
- NF- κ B p65 DNA binding activity (ELISA), phosphorylated and total JNK, phosphorylated AMPK (p-AMPK) total AMPK (Western blotting).
- NF- κ B p65 DNA binding activity (ELISA) & NF- κ B binding activity (Western blotting).
- Phosphorylated and total c-Jun N-terminal kinase
- AMP-activated protein kinase

5.3.14 Domain: Autonomic Nerve Function testing

Timeframe: 0-2 to 12-14 weeks

Description: By Vagus™, a device measuring heart rate and heart rate variability will measure:

Measurements:

- Resting heart rate
- Ratio between minimal and maximal heart rate when the subject is:
 - Rising from supine.
 - Controlled breathing exercises.
 - Doing the Valsalva maneuver.

6 STUDY POPULATION, ANALYSIS SET AND STATISTICAL PRINCIPLES

Eligibility criteria have been previously published³⁵. In brief, the participants suffered from systemic lupus erythematosus, and fulfilled 10 or more points on the 2017 ACR/EULAR SLICC⁴³, were not pregnant, did not suffer from diabetes mellitus and were 18 years or older, both males and females were included.

As stated earlier, sample size calculation required 40 completers, the study included 55 participants.

Randomization was done in a 1:1 ratio, stratified on sex.

The statistical analyses will be carried out primarily in the modified intention to treat (mITT) population, excluding the participants who were randomized but were found ineligible as per the ineligibility criteria within the first week of randomization, while retaining the data from all other study participants as randomized regardless of compliance and study completion. Supplementary per protocol (PP) analyses will exclude data from participants in the exercise group who failed to show up for 80% or more of the exercise sessions (29 or more sessions needed attendance to be considered in the PP group).

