#### 3.2.2 Exclusion criteria

- Health conditions that prevent participating in the exercise intervention determined by the Research Coordinator these include but are not limited to
  - Major bone fracture at inclusion
  - Significant myalgias exacerbated by physical exercise
  - Active infectious disease such as Covid-19
  - Severe symptomatic pleuritis or pericarditis
- Corticosteroid use  $> 10\text{mg/day}$  at baseline
- Diagnosed with diabetes mellitus by physician
- Pregnancy
- SLEDAI-2k (with the SELENA modifications to Proteinuria changes so as to not exclude patients with chronic proteinuria)  $> 10$
- Contraindications to  $^{82}\text{Rb}$ -PET with adenosine stress (according to local guidelines at the Dept. of Clinical Physiology, Nuclear Medicine and PET, Rigshospitalet, which are in accordance with the recommendations of the European Association of Nuclear Medicine)
  - Fever, myocarditis or endocarditis
  - Previous heart transplantation
  - Dysregulated atrial or ventricular tachyarrhythmias
  - Severe chronic obstructive pulmonary disease with a FEV1 of less than 50% of predicted
  - Second or third degree sinoatrial or atrioventricular block
  - Active bronchospasm at the time of the scan
  - Systolic blood pressure  $<90$  or  $>200$  mmHg at the time of the scan

- Treatment with theophyllin within 7 days of the scan

[figure not shown]

Figure 2 Flowchart of study. SLE; Systemic Lupus Erythematosus.

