### 3.3 Intervention

The exercise training program includes three sessions per week over a 12-week period and will take place at CFAS or a local collaborator. The exercise intervention will start when baseline visits have been completed.

[figure not shown]

Figure 3 Exercise intervention, HRMax = Maximal Heart Rate.

The program consists of high intensity endurance training on ergometer bicycles. The intensity will progress throughout the 12 weeks of training. The training consists of 10 minutes of warm up at 40-60% maximum heart rate (HRmax), followed by 4 sets of 4 minutes of high intensity interval training (HR>85%HRmax) followed by 4 sets of 3 minutes of medium intensity (40-60% HRmax), for a total of 28minutes, and finally a 10 min cool-down of 50% HRmax fading to exercise cessation (see sFigure 3 Exercise intervention), for a total exercise time of 38-45 minutes. Previous studies in our centre have had significant results following this training program^17. Strenuous exercise is considered beneficial for SLE patients, and not considered harmful.

All sessions will be supervised and administered by CFAS personnel or local collaborators with experience in handling endurance exercise. To ensure proper intensity, all patients will be wearing a heart rate monitor. The maximal heart rate (HRmax) will be measured as the peak heart rate during the final minute of the VO2max test (see 3.9.2). To evaluate the precise amount of exercise completed for every patient, each training session will be documented (attendance, total time of HRmax > 85%, total time of exercise, average watt, average heart rate, and perceived exertion (BORG scale)).

The exercise session will be counted as successful if more than half of the high intensity training is above 85% of HRmax (so 8 minutes of the session), this is similar to previous studies. The time in each HR span of the patient for each training session will then be recorded to be measured for further compliance parameters.

Control groups will be encouraged to maintain current exercise habits for the duration of the study, and both groups will do a dietary and activity record at study baseline and followup.

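### The primary mITT set drops participants found ineligible in the week after randomisation, without requiring pre-randomisation evidence or arm-blind judgement, and no planned analysis keeps everyone randomised

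*SAP*

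**What the plan says.** SAP section 6 makes the mITT population primary, "excluding the participants who were randomized but were found ineligible as per the ineligibility criteria within the first week of randomization". The same sentence limits the rule, "while retaining the data from all other study participants as randomized regardless of compliance and study completion".

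The only other population is narrower: "Supplementary per protocol (PP) analyses will exclude data from participants in the exercise group who failed to show up for 80% or more" of the sessions. The only sensitivity analysis named for the primary model (SAP 6.1) adds a sex-by-time interaction, which changes the model and not the population.

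Among the exclusion criteria in Protocol 3.2.2 is "Health conditions that prevent participating in the exercise intervention determined by the Research Coordinator", followed by a list that is expressly not exhaustive. Two of its examples carry no time point: "Significant myalgias exacerbated by physical exercise" and "Active infectious disease such as Covid-19". Another is tied to entry: "Major bone fracture at inclusion". The corticosteroid criterion, which is separate, is tied to baseline.

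On contact after allocation, Protocol 3.3 states: "The exercise training program includes three sessions per week over a 12-week period", all supervised. Protocol Table 1 schedules no visit between baseline and follow-up, so controls have no planned contact in that period.

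**The concern.** An exclusion after randomisation is harmless when it rests on a fact that was fixed before allocation and is applied in the same way in both arms. The rule secures neither condition. Its clock runs on when ineligibility is found, and it does not say who decides or whether that person knows the arm.

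The Research Coordinator criterion makes this more than a formality, because it concerns ability to do the training, and the training tests that ability in one arm only. Muscle pain or an infection noticed at a first session could be read as ineligibility in an exerciser, while the same condition in a control would probably go unseen. The Protocol calls the trial investigator-blinded (3.1), but the blinding it describes covers follow-up visits (3.8), validation of echocardiograms (3.9.5) and disease-activity assessment (3.9.11). Eligibility decisions after allocation are not mentioned.

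At stake is the population for both co-primary outcomes. The treatment tests also gate the tests of effect modification by IFNGS (SAP 3.1 and 6.2). If exercisers who tolerate training poorly were removed and similar controls were kept, the comparison would no longer be between the groups as randomised and could lean toward exercise. Maximum likelihood handles missing values of people in the analysis set; it does not bring back people removed from it.

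**Working it through.** **1. Exposure window.** Three sessions a week for 12 weeks is 36 sessions, so one week holds at most about 3 of 36 (8%). This is an upper figure. Protocol 3.3 says only that training starts once baseline visits are complete, and Table 1 places follow-up on day 93 after a last baseline day 4. That is 89 days for an 84-day programme, so the first week after randomisation could hold anywhere from none to about three sessions.

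**2. Inputs for an illustration.**
- VO2max changes from Protocol 3.9.18: control 1.14 (SD 2.15), intervention 3.80 (SD 3.34). The difference is 3.80 − 1.14 = 2.66, which agrees with SAP section 4.
- 55 participants allocated 1:1 (SAP 4 and 6). Assumed split: 27 exercisers, 28 controls.
- Assumed: k participants excluded, all exercisers; a true effect of 2.66 in those kept; the excluded would have had a fraction f of that benefit.

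Neither document gives k, the arm or the reasons.

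**3. Shift in the estimated effect.** If all 27 were analysed, the exercise mean would be lower by

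shift = 2.66 × k × (1 − f) / 27.

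| k | f = 1 (same benefit) | f = 0.5 | f = 0 (no benefit) |
|---|---|---|---|
| 1 | 0 | 0.05 | 0.10 |
| 2 | 0 | 0.10 | 0.20 |
| 3 | 0 | 0.15 | 0.30 |

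Units are ml/kg/min. For example, with k = 3 and f = 0: 2.66 × 3 / 27 = 0.296, so the all-randomised effect would be 2.364 and not 2.66. With 28 exercisers the no-benefit shifts are 0.095, 0.19 and 0.285. Exclusions unrelated to outcome, in either arm or both, give no shift on average.

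**4. Scale.** Using both stated SDs and complete data, the simple two-sample standard error is

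SE = √(3.34²/27 + 2.15²/28) = √(0.413 + 0.165) = 0.760.

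The no-benefit shifts are 0.13, 0.26 and 0.39 SE. The half-width of the planned 97.5% interval is 2.241 × 0.760 = 1.70, so the largest case is 0.296/1.704 = 17% of it.

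**5. Type I error.** In step 3 the shift vanishes if exercise helps nobody, so that illustration is about effect size only. False-positive risk needs a different assumption: that the excluded exercisers would have done worse for reasons other than a missing exercise benefit. Take 28 exercisers and 27 controls, no true effect, and excluded exercisers 1 SD below their arm's mean. The bias in SD units is k/(28 − k), with SE √(1/(28 − k) + 1/27). For k = 3 this is 0.120/0.278 = 0.43 SE. The two-sided error at a nominal 0.025 becomes 0.026, 0.031 and 0.039 for k = 1, 2 and 3.

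**6. FSS.** No effect or SD is given for the FSS, so the second co-primary outcome cannot be illustrated.

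**The case against.** The strongest reply is that being found ineligible under the entry criteria most naturally means not having met them at entry. Later problems have their own routes: session termination (Protocol 3.4), removal for safety (4.9) and withdrawal (4.11). The retention clause keeps those participants in the set. Before allocation everyone also has a medical examination (3.8.2), VO2max tests (3.9.2) and a bout identical to a training session (3.9.3), and SAP 4 places randomisation after these. Most people who cannot tolerate the exercise should have been identified by then. A benign use is easy to picture: baseline classification bloods (3.9.7.1) reported after allocation, in either arm.

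Much of this stands, and it limits the likelihood of bias. It does not supply the missing condition, because the rule does not confine exclusions to such cases.

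Three stronger readings are tempting and should be avoided.
- **Several unanchored criteria.** Myalgia and active infection are examples under the single Research Coordinator criterion, not separate criteria.
- **Exercisers screened for eligibility at every session.** The check before each session (3.4) concerns chest pain only and leads to a call to a doctor, not to an eligibility review.
- **Exclusions hidden from readers.** The SAP plans CONSORT reporting and a flow diagram. What readers would lack is an estimate that includes those excluded.

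The SAP also refers eligibility to a published preprint that is not among the two documents. It may say more about timing or about who decides.

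**Conclusion.** The concern holds as a gap in the rule. The primary set permits exclusions after randomisation that need not rest on pre-randomisation facts or on arm-blind judgement, detection may differ between arms in that week, and no planned analysis keeps everyone randomised.

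A reader might infer that the primary result is biased toward exercise, or that its false-positive rate is inflated. The documents support neither inference. They do not say whether anyone was excluded, from which arm or why, and the error rates in step 5 of the working rest on one-sided exclusions of poor performers that no text describes.

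If one to three exercisers and no controls were excluded, and they would have gained nothing from training, the VO2max effect would be overstated by 0.10 to 0.30 ml/kg/min, at most 0.39 SE. Half the benefit halves these figures. With no exclusions, or with exclusions fixed by facts before allocation, the bias is zero. Priority is minor to moderate: the likely effect is modest, but the rule defines the population for both co-primary outcomes and costs little to tighten.

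**What to change.** Three changes to the SAP before statistical analysis begins:

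1. Limit mITT exclusions to breaches of a listed entry criterion shown by data or samples obtained before randomisation, applied alike in both arms. Results that arrive later from baseline samples would still qualify. The SAP describes enrolment and randomisation in the past tense, so blind judgement now means a re-review: someone without access to allocation or post-randomisation information confirms each exclusion from the pre-randomisation record. Anyone not confirmed returns to the mITT set.
2. Add one sensitivity analysis for the co-primary outcomes, using the same mixed model on all randomised participants as allocated, with any 12-week data available for those excluded.
3. In the CONSORT diagram already planned, show these exclusions by arm and reason.

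The cost is a few lines of wording, a short blinded review and one extra model run per outcome. The sensitivity estimate may be slightly diluted by participants who were truly ineligible. It will add little if those excluded have no 12-week measurements; in that case the tightened rule and the reporting by arm carry most of the value.

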6.1 Statistical Methods

Evaluation of the treatment effect in the primary analyses will be performed using a constrained linear mixed effect model including sex, follow-up time (categorical), treatment, and the constrained treatment*time interaction as fixed effects, and with an unstructured covariance pattern to account for repeated measurements on each study participant; as a sensitivity analysis, the interaction between sex*time will also be considered, but not included in the main model, as there seem to be no interaction for this in exercisers without SLE at 12 weeks⁴⁴. Effect modification by IFNGS will be evaluated by further including IFNGS (continuous scale), the IFNGS- -time interaction, and the constrained treatment*time*IFNGS interaction in the linear mixed model. Missing data will be handled implicitly by maximum likelihood estimation in the linear mixed model.

For the exploratory outcomes in the oral glucose tolerance test and acute exercise bout domains blood was sampled 6 or 9 times (respectively) throughout the measurements, a linear mixed effect model will be used on summary scores (such as DI or Matsuda Index).

